Objectives	
Primary:
 
 • Determine the change in PaO₂/FiO₂ ratio at 0, 24, 48, and 72 hours after implementation of core warming of ventilated patients, and compare this change to patients undergoing standard care. 
Secondary:
 
 • Determine the change in viral load measured in nasopharyngeal swab by Cycle Threshold at 0, 24, 48, and 72 hours after implementation of core warming of ventilated patients, and compare this change to patients undergoing standard care. • Measure the impact of core warming on duration of mechanical ventilation. • Determine impact of core warming on patient mortality.
Number of Participants	22
Length of Participation	72 hour intervention phase; 30 day follow up

Inclusion Criteria	
 1. Patients above the age of 18 years old. 2. Patients with the diagnosis of COVID-19 requiring mechanical ventilation. 3. Patient maximum baseline temperature (within previous 12 hours) < 38.3°C. 4. Patients must have surrogate or legally authorized representative able to understand and critically review the informed consent form.
Exclusion Criteria	
 1. Patients without surrogate or legally authorized representative able to provide informed consent. 2. Patients with contraindication to core warming using an esophageal core warming device. 3. Patients known to be pregnant. 4. Patients with <40 kg of body mass. 5. Patients with DNR status. 6. Patients with acute stroke, post-cardiac arrest, or multiple sclerosis.
Investigational Device	Attune Medical esophageal heat transfer device – ensoETM. Used as indicated for patient temperature management.
Duration of administration	72 hours
Reference therapy	Standard temperature management as routine at study site
Statistical Methodology	A total of 11 patients for each group will be required to yield the necessary pilot data regarding the feasibility and effect of core warming on viral load and ventilation requirements.
Safety Evaluations	Standard adverse event monitoring (device is in widespread use for patient warming and cooling).
Data and Safety Monitoring Plan	The PI and research team will be responsible for data and safety monitoring.

This study will be conducted in full accordance with all applicable study site research policies and procedures and all applicable federal and state laws and regulations.

1.0 Background and Study Rationale

1.1 Introduction

Traditionally, fever has been treated because its metabolic costs were felt to outweigh its potential physiologic benefit in an already stressed host.[1] However, increasing data suggest that fever may be a protective adaptive response that should be allowed to run its course under most circumstances.[2, 3] Although one randomized controlled trial using physical cooling of mechanically ventilated patients with septic shock found a reduction in vasopressor dose and reduced early mortality when treating fever,[4] a growing number of studies have found either no clinically important benefit, or harms, in treating fever of infectious origin.

1.2 Background and Relevant Literature

Studies have found that higher early fever is associated with a lower risk of death among patients with an ICU admission diagnosis of infection [5, 6] and that fever may enhance immune-cell function,[7, 8] inhibit pathogen growth,[9-11] and increase the activity of antimicrobial drugs.[12] Fever potentially benefits infected patients via multiple mechanisms; in vitro and animal studies have shown that elevated temperatures augment immune function, increase production of protective heat shock proteins, directly inhibit microorganism growth, reduce viral replication, and enhance antibiotic effectiveness.[3, 13] More rapid recoveries are observed from chickenpox,[14] malaria,[15] and rhinovirus [16] infections with avoidance of antipyretic medication, and many innate and adaptive immunological processes are accelerated by fever.[17-19] The UK National Institute for Health and Care Excellence (NICE) recommend not using antipyretic agents “with the sole aim of reducing body temperature in children with fever.”[17, 20] As recently as the 1910’s, the “malaria fever cure” (inducing fever to treat a range of conditions, an approach known as “pyrotherapy”) was widespread, with the originator of the idea receiving the Nobel Prize in Medicine or Physiology in 1927.[21, 22]

A randomized control trial published in 2005 evaluating the impact of antipyretic therapy on outcomes in critically ill patients had to be terminated at the interim analysis as there were seven deaths in the aggressive group and only one death in the permissive group.[23] Another randomized controlled trial in critically ill patients (without neurotrauma or severe hypoxia) failed to support the treatment of fever; no significant differences in ICU and hospital length of stay, or mortality between those receiving external cooling for temperature ≥ 38.5 °C vs. no antipyretic treatment was found.[24] A prospective controlled trial randomized 700 patients with fever of known or suspected infectious etiology to receive either 1 g of intravenous acetaminophen or placebo every 6 hours until ICU discharge, resolution of fever, cessation of antimicrobial therapy, or death.[25] The primary outcome, ICU-free days until day 28, was not decreased in the treatment arm, and secondary outcomes (28 and 90-day mortality, ICU and hospital length of stay) were also not significantly different between groups.[25]

A systematic review and trial sequential analysis of randomized controlled trials found a total of 6 randomized controlled trials including 819 patients.[26] Overall, there was no beneficial effect of antipyretic therapy on mortality risk in patients with established sepsis (OR: 1.02, 95% CI:

0.50–2.05), and the review failed to identify any beneficial effect of antipyretic therapy on ICU patients with established diagnosis of sepsis.[26] Another systematic review and meta-analysis of randomised controlled trials investigating treatments administered to febrile patients found fifteen studies reporting results from 13 trials, and found that active temperature management neither increased nor decreased mortality risk, ICU, or hospital length of stay in critically ill adults.[27] A meta-analysis examining the impact of antipyretic therapy on mortality in critically ill septic adults found 8 randomized studies (1,507 patients) and 8 observational studies (17,432 patients).[28] Antipyretic therapy did not reduce 28-day/hospital mortality in the randomized studies (relative risk, 0.93; 95% CI, 0.77–1.13; $I^2 = 0.0\%$) or observational studies (odds ratio, 0.90; 95% CI, 0.54–1.51; $I^2 = 76.1\%$), and the authors concluded that antipyretic treatment does not significantly improve 28-day/hospital mortality in adult patients with sepsis.[28]

A retrospective cohort study evaluated 1,264 patients requiring mechanical ventilation initiated in the ED with subsequent admission to an intensive care unit.[29] The authors found that high fever ($\geq 39.5^{\circ}\text{C}$) was associated with increased risk for mortality in mechanically ventilated patients; however, in patients with sepsis, moderate fever (38.3°C – 39.4°C) was protective, and antipyretic medication was not associated with changes in outcome.[29] An open, parallel-group pilot randomized clinical trial (the FEVER pilot trial) enrolled 87 pediatric intensive care unit patients who were randomly assigned to permissive (antipyretic interventions only at $\geq 39.5^{\circ}\text{C}$) or restrictive groups (antipyretic interventions at $\geq 37.5^{\circ}\text{C}$) whilst on respiratory support.[17] Length of stay, duration of organ support and mortality were similar between groups, and no pre-specified serious adverse events occurred.[17] Finally, a pilot study of external warming of septic patients ([ClinicalTrials.gov](https://clinicaltrials.gov) Identifier: NCT02706275) has recently been completed, with initial analysis of results appearing promising (manuscript in preparation).

Temperature has been suggested to influence the virulence of an earlier discovered coronavirus, SARS CoV, [30] and most isolates of human rhinovirus, the common cold virus, replicate more robustly at the cool temperatures found in the nasal cavity (33 – 35°C) than at core body (lung) temperature (37°C).[31] Rhinovirus replicates preferentially at cooler nasal cavity temperature due, in part, to a less efficient antiviral defense response of infected cells at cool temperature, raising the possibility that inhaling cool air might diminish resistance to respiratory virus infections by lowering the temperature of potential host cells lining the nasal cavity.[31] Influenza

B virus viral hemagglutinin exhibits higher expression at 33°C (a temperature required for membrane fusion), indicating pronounced adaptation to the mildly acidic pH and cooler temperature of human upper airways.[32] Specifically, protein expression of influenza B virus viral hemagglutinin proved to be temperature dependent, with expression highest at 33°C and gradually decreasing at higher temperatures.[32] On the other hand, avian influenza A viruses, adapted to the temperature of the avian enteric tract (40°C), show restricted growth at cooler temperatures ($\sim 32^{\circ}\text{C}$).[32]

More recently, simulations of the receptor binding domain (RBD) of SARS-CoV-2 found that it is more flexible than SARS CoV, especially near the binding site, suggesting that the RBD will have a higher entropy penalty upon binding angiotensin-converting enzyme II (ACE2) compared to the RBD of SARS-CoV.[33] Consequently, SARS-CoV-2 may be more temperature-sensitive in terms of human infection than SARS-CoV.[33]

Hyperthermia induced by directly heating the body (as opposed to fever induced by introducing bacterial extracts or other foreign substances) is normally limited to 41.8 to 42°C when used to kill tumor cells in cancer treatment, with minimal adverse effects.[34-37] Furthermore, hyperthermia and elevated temperature have been found to have positive impacts on the immune system. Cells have been found to exhibit increased levels of heat-shock proteins, specifically HSP70 [38] and HSP90, [39] which are directly related to and/or cause antigen presentation and cross-presentation, activation of macrophages and lymphocytes, and activation and maturation of dendritic cells,[40] all of which are essential antiviral immune responses. Notably, fever has often abated by the time a COVID-19 patient requires mechanical ventilation.[41]

The aim of this study is to determine the effect of active core warming patients diagnosed with COVID-19 and undergoing mechanical ventilation. We hypothesize that active core warming will reduce the severity of acute respiratory distress syndrome, reduce the duration of mechanical ventilation, and improve survival compared to standard of care.

1.3 Name and Description of the Core Warming Device

Core warming will be performed using an esophageal heat transfer device (ensoETM, Attune Medical, Chicago, IL) This device is an FDA cleared device, and is a multi-lumen silicone tube placed in the esophagus for the purpose of cooling or warming a patient while simultaneously allowing gastric decompression and drainage. Modulation and control of the patient's temperature is achieved by connecting the device to an external heat exchanger. Two lumens connect to the external heat exchanger, while a third central lumen provides stomach access for connection to a fluid collection device with low intermittent suction for gastric decompression. Distilled water circulates within the device just like a water blanket. The device can be placed by most providers in the operating room, emergency room, or intensive care unit. It is a single-use, disposable, non-implantable device with an intended duration of use of 72 hours or less. For this study, the device will be used during mechanical ventilation of patients with diagnosed COVID-19, under the intended indication of patient temperature management as detailed in the product instructions for use.

1.3.1 Clinical Data to Date

Core warming and cooling has been used safely in thousands of patients for temperature control, making it the ideal approach to use for this study. Core cooling or warming using an esophageal heat transfer device is used for a range of temperature management purposes, including post-cardiac arrest therapeutic hypothermia [42-45], warming of burn patients [46], warming general surgical patients,[47] cooling traumatic brain injury,[48] cooling heat stroke,[49] and the treatment of central fever.[50, 51]

2 Study Objectives

The purpose of the proposed pilot study is to determine if core warming improves respiratory physiology of mechanically ventilated patients with COVID-19, allowing earlier weaning from ventilation, and greater overall survival.

2.1 Primary Objectives

1. Determine the change in PaO₂/FiO₂ ratio at 0, 24, 48, and 72 hours after implementation of core warming of ventilated patients, and compare this change to patients undergoing standard care.

2.2 Secondary Objectives

1. Determine the change in viral load measured in nasopharyngeal swab by Cycle Threshold at 0, 24, 48, and 72 hours after implementation of core warming of ventilated patients, and compare this change to patients undergoing standard care.
2. Measure the impact of core warming on duration of mechanical ventilation.
3. Determine impact of core warming on patient mortality.

3 Investigational Plan

3.1 General Design

This is a small scale pilot study to evaluate if core warming improves respiratory physiology of mechanically ventilated patients with COVID-19, allowing earlier weaning from ventilation, and greater overall survival. This prospective, randomized study will include 22 patients diagnosed with COVID-19, and undergoing mechanical ventilation for the treatment of respiratory failure. Patients will be randomized in a 1:1 fashion with 11 patients (Group A) randomized to undergo core warming, and the other 11 patients (Group B) serving as the control group who will not have the ensoETM device used. Patients randomized to Group A will have core warming initiated in the ICU or other clinical environment in which they are being treated after enrollment and provision of informed consent from appropriate surrogate or legally authorized representative.

3.1.1 Screening Phase

Subjects will be recruited from the ICU or other clinical environment in which they are being treated (Emergency Department, step-down unit, etc.). Patients will be identified by the PI or other study investigators/coordinators as available. All patients without a DNR order with a diagnosis of COVID-19 and meeting inclusion criteria will be eligible for screening for any exclusion criteria. Written informed consent for the research study will be obtained from patient's surrogate or legally authorized representative prior to enrollment.

3.1.2 Study Intervention Phase

Participants who have a signed research study consent form (via surrogate or legally authorized representative) will be randomized in a 1:1 fashion to core warming with the study device (ensoETM) or to standard of care (standard temperature management and treatment). The device will be used as indicated (for warming). Patient temperature measurement will be collected for both the core warming and standard of care arms during the study period (72 hours).

Core warming will be performed using standard technique per instructions for use for the esophageal heat transfer device. The esophageal heat transfer device will be set to 42°C temperature after initial placement, and maintained at 42°C for the duration of treatment. It is expected that patient temperature will increase from baseline by 1°C to 2°C, but due to ongoing

heat loss from the patient, the expected maximum patient temperature is below 39°C. The time course of illness of COVID-19 is such that most patients no longer have fever by the time of mechanical ventilation.[41] If patient temperature increases above this range and reaches 39.8°C, the device will be set to an operating temperature of 40°C, thereby preventing any further increase in patient temperature (ambient heat loss precludes patient from reaching device operating temperature).

Monitoring and Evaluation

All patients will have usual standard of care labs, vital signs, and imaging for patients undergoing mechanical ventilation in the ICU. Specific parameters to be measured include PaO₂ at regular intervals appropriate for patients undergoing mechanical ventilation, and FiO₂ at the time of obtaining blood gases for PaO₂ measurement, to allow calculation of P/F ratio.

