5.1 Intervention Regimen

Patients who are randomized to core warming will have the esophageal heat transfer device placed in the ICU or other treatment area where patient is undergoing mechanical ventilation. The device will remain in place until the study is completed (72 hours). The device will be set to 42°C for the duration of the study period, with the exception of any elevations in patient temperature as described in section 3 above.

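### The 40°C step-down at 39.8°C is said to stop any further rise, but its stated reason supports only a ceiling below 40°C, and no further temperature-triggered step is written

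*Combined protocol and SAP*

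**What the plan says.** Section 3.1.2 of the combined protocol and SAP starts the device at 42°C, "maintained at 42°C for the duration of treatment". Its forecast has two parts: "It is expected that patient temperature will increase from baseline by 1°C to 2°C", and, because heat is lost from the patient, "the expected maximum patient temperature is below 39°C". It adds that "most patients no longer have fever by the time of mechanical ventilation".

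The contingency follows. If the patient goes above this range and reaches 39.8°C, "the device will be set to an operating temperature of 40°C, thereby preventing any further increase in patient temperature". The reason given is that "ambient heat loss precludes patient from reaching device operating temperature".

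Other sections bear on the same point:

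- Section 4.1 admits patients whose maximum temperature in the previous 12 hours was below 38.3°C.
- Section 5.1 keeps the device in place for 72 hours at 42°C, "with the exception of any elevations in patient temperature as described in section 3 above". It adds no step of its own.
- Section 6.3 (Rescue Therapy) provides for removing the device on malfunction only.
- Section 6.5 lets the investigator discontinue or withdraw a subject for adverse events, safety or clinical necessity. It names no temperature.

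**The concern.** The rule is credited with an effect that its own figures do not give. It acts when the patient is at 39.8°C and the device goes to 40°C. The printed reason is that the patient stays below the device temperature. Staying below 40°C is not the same as not rising from 39.8°C.

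The reason also considers only device heat and loss to the room. A patient producing fever is outside it, and the section does not exclude such patients. Eligibility looks back 12 hours, while warming runs for 72.

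What is at stake is how staff act once the trigger is met. By then the temperature is already at least 0.8°C above the forecast maximum (39.8 - 39.0). The text tells them that the reset has dealt with the problem, and gives no temperature-based instruction if it has not. Section 1.2 cites a cohort in which fever of 39.5°C or more was associated with higher mortality in ventilated patients, and the plan does not relate its 39.8°C trigger to that figure. The evidence is observational and no threshold is inferred from it here.

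**Working it through.** **Inputs.** From section 3.1.2: trigger 39.8°C, device 42°C before and 40°C after the step, expected rise 1 to 2°C, forecast maximum below 39°C. From section 4.1: baseline below 38.3°C.

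**1. Does the stated reason give the stated effect?**

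- Claimed further rise after the step: none.
- Ceiling supported by the reason: patient temperature below 40°C.
- Difference: 40.0 - 39.8 = 0.2°C, so the reason leaves room for just under 0.2°C above the trigger. The claim of none is not reproduced.
- Device minus patient before the step: 42.0 - 39.8 = 2.2°C. After it: 0.2°C, about 9% of the earlier gap (0.2 / 2.2 = 0.091).

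**2. Would the temperature actually rise?** The documents give no heat-balance figures, so this is an illustration on assumed values. Let D be the device temperature, S the temperature at which the patient would settle without the device, and w the device's share of heat exchange (assumed 0.1 to 0.5). Then

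T = w × D + (1 - w) × S.

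Lowering D from 42 to 40°C lowers T by 2w, that is by 0.2 to 1.0°C. With D = 40°C:

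| S (°C) | T at w = 0.1 | T at w = 0.5 |
|---|---|---|
| 37.0 | 37.30 | 38.50 |
| 39.0 | 39.10 | 39.50 |
| 39.8 | 39.82 | 39.90 |
| 40.5 | 40.45 | 40.25 |

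T exceeds 39.8°C when S > (39.8 - 40w) / (1 - w). At w = 0.5 this is 19.8 / 0.5 = 39.6°C; at w = 0.1 it is 35.8 / 0.9 = 39.78°C. T exceeds 40°C when S exceeds 40°C. So for S of 39.0°C or less the patient settles below the trigger and the step does what is wanted. With S of about 39.6 to 39.8°C or more, which means marked fever of the patient's own, the assurance fails. Above 40°C the printed reason fails too.

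**3. Can the trigger be reached on the plan's own forecast?**

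| Baseline (°C) | plus 1°C | plus 2°C |
|---|---|---|
| 36.5 | 37.5 | 38.5 |
| 37.0 | 38.0 | 39.0 |
| 37.8 | 38.8 | 39.8 |
| 38.0 | 39.0 | 40.0 |
| just under 38.3 | about 39.3 | about 40.3 |

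A baseline of 37.8°C with the upper expected rise lands on the trigger. From 37.0°C the upper rise is no longer below 39°C, and from 38.0°C even the lower rise is not.

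**4. What follows the step?** Section 3.1.2 ends its temperature rule at the 40°C setting. Section 5.1 refers back to it, section 6.3 concerns malfunction, and section 6.5 gives discretion without a temperature criterion. The schedule in section 6 lists temperature monitoring without an interval.

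**The case against.** The best defence is that the sentence concerns net heat balance and is right for the case it has in mind. The reset removes about 91% of the device-to-patient gap while loss to the room continues. In the illustration the settling temperature always falls, and it ends above the trigger only when the patient's own fever is high. This stands. A reader might infer that the device alone would push the patient up by almost 0.2°C. The documents do not support that: 0.2°C is the distance between the claim and the ceiling its reason supports.

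Three other inferences go too far:

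- That the heat-balance premise has already failed at the trigger. The premise is that the patient stays below the device temperature, and 39.8°C on a 42°C device satisfies it. What has been exceeded is the forecast maximum.
- That nothing at all can follow the step. Section 6.5 allows discontinuation for adverse events, safety or clinical necessity, and temperature is measured in both arms for 72 hours. What is missing is a written temperature criterion. Section 3.1.2 also invokes the device's instructions for use, which are not available here, so any limits in them are unknown.
- That surrogates were given this assurance. The consent pages are not available, and the risk section (11.1) does not repeat it.

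It can also be said that the forecast maximum is meant to override the 1 to 2°C range, since the section joins the two by reference to heat loss. That is a possible reading. But the section does not say that the expected rise shrinks at higher baselines, and from 38.0°C upward even 1°C does not fit.

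None of this repairs the wording. The assurance is unconditional, while its reason is neither exact at 39.8°C nor applicable to endogenous fever.

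**Conclusion.** The point holds as a contradiction between a stated safety effect and the reason given for it. The assurance exceeds its reason by up to just under 0.2°C when the device is the only added heat source. It has no support when the patient's own fever is high: about 39.6 to 39.8°C without the device, under the assumed heat balance with w from 0.1 to 0.5. The assurance is attached to the only written temperature-triggered step in the warmed arm.

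The forecast maximum below 39°C also conflicts with the eligible baseline plus the expected rise, which reaches about 40.3°C, so the contingency is not remote on the plan's own figures.

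The first and last of these results need only the protocol's numbers. The fever threshold depends on assumed values and is illustrative. No rate of reaching 39.8°C can be derived from the documents. Because the matter bears on patient safety and costs little to correct, it should be corrected rather than left to interpretation.

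**What to change.** Amend section 3.1.2 to remove or correct the statement that the 40°C setting prevents any further increase. Reconcile sections 3.1.2, 4.1, 5.1, 6.3 and 6.5 so that the baseline limit, expected rise, forecast maximum, trigger, reduced setting and intended effect agree, and so that the plan says what follows if the temperature continues to rise after the step. The existing cross-reference in section 5.1 is enough once section 3.1.2 is right. All values and clinical rules are for the sponsor and investigator to choose.

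Add to data collection the time of each device setting change and the patient temperature after it. Section 6.2.2 lists ventilator settings but not device settings, so the warming actually delivered in Group A could not otherwise be described.

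The cost is a short amendment with IRB submission and a few extra data fields. It needs no added patients or procedures.
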